### 5.1 Informed Consent

Prior to any non-standard-of-care procedures, the patient must sign the Informed Consent Form (ICF) approved by the Ethics Committee (EC). All patients will be informed in detail about the nature of the clinical investigation, as well as its risks, potential benefits, and any anticipated discomforts. The Investigator or assigned designee must administer the ICF to each prospective study patient, and obtain the patient's signature or a legally authorized representative signature along with the date of consent. Proper informed consent should be obtained in accordance with local/country guidelines as needed.

### 5.2 Screening Evaluation

All patients considered for enrollment must undergo a thorough screening evaluation prior to the scheduled vascular access creation procedure. The screening evaluation includes:

- Collection of demographic data;
- A medical history and physical exam;
- A duplex ultrasound and optional angiography/venography assessment;
- Pregnancy test (if of child bearing potential (urine or blood))

There will be a final determination of the patient's study eligibility due to vascular anatomy made at the time of the index procedure and thus, there may be some consented patients who are determined to be ineligible to participate in the study thus who will not undergo the everlinQ endoAVF procedure. All patients that sign the study ICF and do not undergo the everlinQ procedure will be considered screen failures.

The status of all patients screened should be captured on the study Subject Screening Log for tracking and reporting purposes.

### **5.2.1 Duplex Ultrasound**

A duplex ultrasound (DUS) assessment of the flow rates and inner diameters of the arteries and veins of the target vessels must be performed per the study Duplex Ultrasound Guidelines. Sites should ensure that only DUS operators who are trained on the protocol and DUS guidelines are performing these tests.

## **5.3 Medications**

There are no required medications in the study however, it is recommended that an antiplatelet medication be administered as a loading dose prior to the study procedure and continue daily for at least 1-month post study procedure.

A Medication Log (eCRF) will be completed and maintained from Screening through 12 month follow up on the use of Hypertension Medications.

### **5.3.1 Intra-Procedure**

All patients must receive adequate anticoagulation according to hospital standard practice. It is recommended that an activated clotting time (ACT) test be administered after the initial dose of anticoagulant therapy to verify an ACT  $\geq$  225 seconds prior to the insertion of the study device.

### **5.3.2 Study Procedure**

If a study candidate presents for the index procedure with any medical condition that precludes treatment, the procedure should be delayed until the infection or medical condition is treated and resolved.

The everlinQ endoAVF System should be used per package labeling and the most current Instruction for Use (IFU) for the system selected. Procedural steps for the everlinQ procedure are outlined in the specific IFU and supporting training materials. All elements of the procedure are consistent with other endovascular procedures.

Only about 10cc of diluted contrast agent is required for the entire everlinQ procedure which is similar to other AVF interventions performed on pre-dialysis patients.

Alternatively, CO2 contrast can be used for venography/angiography as determined by the treating physician.

### **5.3.3 Post-Treatment**

After the treatment with the everlinQ endoAVF system, the arterial and venous puncture sites should be closed per standard hospital procedures, and it is recommended that manual compression is held for 20 minutes.

**Note:** TVA Medical does not recommend the use of arterial closure devices to obtain hemostasis in subjects treated with the everlinQ system.

## **5.4 Follow-Up Visits**

All enrolled patients that undergo a successful endoAVF creation will return for follow-up at 0-10 days post index procedure, then again at 21-45 days, 3, 6, and 12 months post index procedure. Refer to Table 1 for required testing at each follow-up visit.

### **5.4.1 Dialysis Access Data**

Once hemodialysis is first initiated via the endoAVF (1 or 2- needle cannulation), detailed dialysis access data will be collected until 2/3 of the dialysis sessions are successfully performed using the endoAVF with 2- needle cannulation for over a continuous 28-day period.

## **5.5 Unscheduled Visit**

In addition to scheduled follow-up visits, the patient should be instructed to contact the Investigator at any time during the follow-up period if he/she has questions or concerns relating to the procedure or the vascular access. If the patient returns to the clinic for evaluation related to his/her participation in the study between scheduled follow-up visits (i.e., not a study required visit):

- No adverse events noted during unscheduled visit – no forms need to be completed.
- Adverse event noted – The Adverse Event (AE) eCRF is required to be completed for each event.
- Intervention to maintain or restore patency of the fistula, to support maturation of the arterialized vein segments, or to support cannulation of the arterialized vein segments – the Post-Procedure Intervention eCRF must be completed.

The patient will still be required to return for the next scheduled follow-up visit if the unscheduled visit is out of the compliance follow-up window.

If the patient is treated by a health-care professional other than the Investigator for treatment-related complications, the Investigator must request copies of the medical records and, if necessary, complete the appropriate eCRFs.

## **5.6 Lost to follow-up**

If an enrolled patient fails to comply with follow-up evaluations and misses two (2) consecutive follow-up visits with failure of all contact attempts, the patient may then be considered lost to follow-up and exited from the study. Please contact TVA Medical to discuss any patients who

may be lost to follow-up, prior to exiting the patient from the study. Data collected prior to the study exit will be included in the analysis. All missed follow-up visits must be documented on a Protocol Deviation eCRF.

### **5.7 Patient Withdrawal from the Study**

Patients can voluntarily withdraw from the study at any time for any reason; the reason for withdrawal will be documented on the End of Study eCRF. All available data at the time of withdrawal (if any) will be used for analysis. Table 5-2: Withdrawal and Follow-Up Requirements summarizes the required actions and follow-up for patients who may have to be withdrawn from the study for varied reasons.

**Table 5-2: Withdrawal and Follow-Up Requirements**

If	Action Item
ICF was signed and the study catheter was not inserted.	The patient is not considered enrolled. Complete the Subject Screening Log as a screen failure.
The study catheter was inserted but RF energy was not delivered and therefore, the patient did not undergo endoAVF procedure (e.g., index procedure was aborted or converted to other surgical methods for AVF creation).	The patient is not considered enrolled. Complete the Subject Screening Log as a screen failure.
The study catheter was inserted and RF energy was delivered but the endoAVF was not created, with or without a reportable adverse event(s).	Patient is considered enrolled. Follow patient until protocol reportable AE resolves.  Collect all baseline-procedure and adverse event data and exit the patient (end date = date of AE resolution).
The study catheter was inserted and RF energy was delivered and endoAVF was successfully created.	Patient is considered enrolled. Follow all required visits per Study Protocol.
endoAVF was successfully created (patient enrolled) and there is a permanent loss or abandonment of the endoAVF	Patient participation ends. Complete Follow up forms as appropriate until loss of endoAVF, then complete an End of Study eCRF.

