## **4 STUDY METHODOLOGY**

### **4.1 Study Design**

This is a prospective, multi-center study to evaluate the everlinQ endoAVF System when used to create an endoAVF for patients who require vascular access for hemodialysis. This study is a post-market study, and will be available to sites in selected regions where the product is available for use and properly registered or licensed (i.e. CE Mark, Health Canada License).

The study may have up to 20 active sites participating in order to enroll up to 200 patients that undergo endoAVF creation with the everlinQ endoAVF System. All patients who meet study inclusion criteria and no exclusion criteria will be considered a study candidate. Study candidates who undergo the everlinQ procedure (catheter insertion and delivery of RF energy) will be enrolled in the study. Study candidates who do not undergo the everlinQ procedure will be treated per physician and hospital guidelines and will not be considered enrolled in the study. All enrolled patients are expected be followed up to 12 months. Refer to Figure 1 for a flowchart overview of the study, and Table 2 for Withdrawal and Follow-Up Requirements.

**Figure 1: Study  
Flowchart**

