## **4.3 Study Outcome Measures**

All patients enrolled in the study and do not have a renal transplant, will be included in these outcome measurements unless otherwise noted.

**Primary Patency:** The interval from the time of access placement until any intervention designed to maintain or re-establish patency, access thrombosis, access abandonment, or the time of measurement of patency.

❖ **endoAVF abandonment definition:**

The endoAVF is considered abandoned if any of the following occur:

- The endoAVF is occluded and patency cannot be restored by any intervention, including medical, surgical, radiological or rest through the last follow up;
- The endoAVF is deemed inadequate for dialysis (for example, it never matures or is too deep for needle access) and the associated problem cannot be corrected by any intervention, including medical, surgical, radiological or rest;
- The endoAVF is ligated.

An endoAVF is not considered abandoned when it is not cannulated in subjects with a successful renal transplantation or when reasons of subject preference alone preclude cannulation.

**Assisted Primary Patency:** The interval from access placement to thrombosis or abandonment; not triggered by access circuit interventions performed in the absence of occlusion.

**Secondary Patency:** The interval from the time of access placement until access abandonment, loss to thrombosis, or the time of patency measurement including intervening manipulations (surgical or endovascular interventions) designed to re-establish functionality in thrombosed access.

**Functional Patency:** The interval of time from the first 2-needle dialysis utilizing the access until access abandonment.

**Procedure Success:** The successful creation of an endoAVF with blood flow confirmed intraoperatively by fistulography or by duplex ultrasound postoperatively.

**Time to Endovascular Fistula (endoAVF) Maturation (Vascular Access Usability):** Total time (number of days) from successful endoAVF creation to one of the following:

- Successful hemodialysis using 2 needle cannulation ***OR***
- Vascular accesses that is free of stenosis or thrombosis, with brachial artery flow of at least 500 ml/min and at least a 4.0 mm vein diameter as measured via duplex ultrasound.

**Time to Cannulation:** The time (number of days) from the index procedure (successful endoAVF creation) to the first use of the endoAVF for cannulation will be reported.

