## **6.1 Relationship to Device or Procedure**

The Investigator will also evaluate the relationship of the adverse event to the everlinQ endoAVF System or procedure according to the following definitions:

**Definite (YES):** The AE follows a reasonable timing from treatment (or attempted treatment) with the device and the possibilities of factors other than the device or the index procedure, such as underlying disease, concomitant drugs, or concurrent treatment can be excluded. This includes an AE that occurs during the index (endoAVF creation) procedure.

**Probable (YES):** The AE follows a reasonable timing from treatment (or attempted treatment) with the device and the probability of device or procedure involvement cannot be excluded. However, other factors such as underlying disease, concomitant medications, or concurrent treatment may be possible.

**Unlikely (NO):** The AE follows an unlikely timing relationship from treatment (or attempted treatment) or is more likely due to other factors and there is no definitive information suggesting that it was related to the device or procedure.

**Not Related (NO):** The AE has no timing relationship from treatment (or attempted treatment) or it can be explained by other factors, including underlying disease, concomitant medication, or concurrent treatment.

The Investigator will evaluate the relationship to the everlinQ device portion of the procedure using the yes/no definitions above. The everlinQ device portion of the procedure only includes insertion, deployment and removal of the everlinQ catheters.

All reported adverse events will be reviewed and adjudicated by an independent Clinical Events Committee (CEC).

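### Attempts that stop after catheter insertion but before RF are not enrolled, so Procedure Success is conditional on RF delivery and adverse events in these patients stay out of the reported rate

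*Combined protocol and SAP*

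**What the plan says.** Section 4.1 makes RF delivery a condition of enrollment: "Study candidates who undergo the everlinQ procedure (catheter insertion and delivery of RF energy) will be enrolled in the study". Section 5.2 is consistent with this: "All patients that sign the study ICF and do not undergo the everlinQ procedure will be considered screen failures". Table 5-2 then separates four situations before or at fistula creation:

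- **Row 1, catheter not inserted:** not enrolled, Screening Log entry.
- **Row 2:** "The study catheter was inserted but RF energy was not delivered and therefore, the patient did not undergo endoAVF procedure". The examples are abortion of the procedure or conversion to a surgical method. Not enrolled, and the same Screening Log entry as row 1.
- **Row 3, RF delivered but no endoAVF created:** enrolled. The instruction is "Collect all baseline-procedure and adverse event data and exit the patient".
- **Row 4, endoAVF created:** enrolled, full follow-up.

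Section 4.3 sets the analysis population: "All patients enrolled in the study and do not have a renal transplant, will be included in these outcome measurements unless otherwise noted". It defines Procedure Success as "The successful creation of an endoAVF with blood flow confirmed intraoperatively by fistulography or by duplex ultrasound postoperatively". Neither Procedure Success nor the Adverse Events measure names a different denominator, so the enrolled set applies to both.

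**The concern.** Procedure Success should show how often an attempt with the device produces a fistula. Section 2 describes insertion and alignment of the two catheters as steps that come before RF. A failure at either step would therefore fall in row 2 and leave the denominator. What is reported is success given that RF was delivered, and the plan requires no figure from which a reader could recover success per attempt.

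The same rule affects safety. Row 2 patients have had the study catheter in a vessel. Section 3.2 lists an aborted procedure among the risks. Section 6.1 extends relatedness to treatment that was only attempted and says: "The everlinQ device portion of the procedure only includes insertion, deployment and removal of the everlinQ catheters". An insertion injury that ends the procedure fits those definitions, yet row 2 asks for no adverse event data. Insertion injuries in patients who go on to RF are kept.

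Section 4.2 says the data may support reimbursement and publications. With no hypothesis test (Section 7), the descriptive estimates are the study's whole output.

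**Working it through.** **Inputs.** From the documents: up to 200 treated patients (Protocol Summary), enrollment on RF delivery (Section 4.1), and outcomes in enrolled patients (Section 4.3). The documents give no target success rate, no expected abort share and no expected event rate, so there is no planned figure to reproduce. Assumed for illustration: a no-RF share *k* of catheter insertions of 2%, 5% or 10%; successes of 196/200 or 190/200; serious related events in 6/200 enrolled patients.

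**Direction for Procedure Success.** A patient who receives no RF cannot have an endoAVF created by the device. With *s* successes among 200 enrolled and *m* no-RF attempts, the reported rate is *s*/200 and the per-attempt rate is *s*/(200 + *m*). The second can never exceed the first. The ratio of reported to per-attempt is 1/(1 − *k*): 1.02, 1.05 and 1.11.

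**Size.** *m* = 200*k*/(1 − *k*) gives 4.1, 10.5 and 22.2, rounded to 4, 11 and 22.

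| Assumed *k* | *m* | Reported 196/200 = 98.0%; per attempt | Reported 190/200 = 95.0%; per attempt |
|---|---|---|---|
| 2% | 4 | 196/204 = 96.1% | 190/204 = 93.1% |
| 5% | 11 | 196/211 = 92.9% | 190/211 = 90.0% |
| 10% | 22 | 196/222 = 88.3% | 190/222 = 85.6% |

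**Against sampling error.** The exact (Clopper-Pearson) 95% interval for 196/200 is 95.0% to 99.5%. With 6 no-RF attempts, 196/206 = 95.1%, still inside. With 7 (*k* = 7/207 = 3.4%), 196/207 = 94.7%, below it. The two rates estimate different quantities, so this is only a yardstick: under these assumptions a handful of omitted attempts shifts the figure by more than the interval would suggest.

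**Anatomical ineligibility.** Section 5.2 provides for a final determination of "study eligibility due to vascular anatomy made at the time of the index procedure". Some row 2 cases may therefore be ineligible patients, not device failures. If 5 of 11 no-RF cases were ineligible, the rate among eligible attempts would be 196/206 = 95.1%, not 92.9%. The table is thus an upper bound on the gap if the question is limited to eligible patients.

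**Adverse events.** With 11 no-RF patients at risk *r*, the per-attempt rate is (6 + 11*r*)/211, against 6/200 = 3.0% reported:

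- *r* = 0: 6/211 = 2.8%
- *r* = 3%: 6.33/211 = 3.0%, unchanged
- *r* = 10%: 7.1/211 = 3.4%
- *r* = 20%: 8.2/211 = 3.9%

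Any event in these patients makes the count incomplete. The rate is understated only if their risk exceeds that of enrolled patients.

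**The case against.** The strongest reply is that the rule is open and consistent. Sections 4.1 and 5.2 and Table 5-2 agree, and the Protocol Summary counts treated patients, so success among RF-treated patients is a legitimate, stated population. That is true, and it makes this a design choice and not an inconsistency. But stating a denominator does not supply the per-attempt rate.

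Second, other routes may catch these patients. Section 5.2 requires the Screening Log to hold the status of everyone screened, and Table 8-1 does not restrict serious event reports to enrolled patients. Row 2 does not forbid collecting adverse events, and Section 4.3 does not say that only enrolled patients count. So some information may reach the sponsor. However, rows 1 and 2 get the same log entry, the protocol text does not require a separate count or a reason, and nothing places these patients or their events in a reported rate.

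Third, the conflict with Section 6.1 is mild. Attempted treatment could refer to row 3, and the device-portion sentence serves relatedness, not enrollment. This is fair: the passages fit poorly but do not contradict each other outright.

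Fourth, a per-attempt rate mixes ineligible anatomy with device failure, and all the magnitudes rest on assumed inputs. Both points stand. They argue for showing both rates with reasons, not for replacing the current one.

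**Conclusion.** The concern holds. Followed as written, the plan gives a Procedure Success rate that omits attempts that are failures by definition, and the bias runs one way. It equals *k* times the reported rate: for a reported 98.0%, 0.98 × 2% = 2.0 points up to 0.98 × 10% = 9.8 points over the assumed range. It is smaller if aborts are rare or mostly reflect ineligible anatomy, but the plan requires no report that would show either. For adverse events, the reported count omits any event in a no-RF patient; the direction of the effect on the rate is not known. The point affects one descriptive measure and the adverse event summary in a study with no hypothesis test and no designated primary outcome. It should be fixed, and it does not touch patency or maturation.

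**What to change.** 1. Amend row 2 of Table 5-2 so that baseline, procedure and adverse event data are collected as in row 3. These patients can remain outside the enrolled set.
2. In Section 4.3, define a device-attempted set: every consented patient with a study catheter inserted. Report Procedure Success and serious device- or procedure-related events on this set beside the enrolled set.
3. Report the number of no-RF patients and the reason for each, separating anatomical ineligibility found at the index procedure from device or procedure failure.
4. Keep patency, maturation and the cap of 200 treated patients as they are.
5. Reconcile row 2 with the attempted-treatment and device-portion wording of Section 6.1.

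The cost is a short amendment and a few eCRF pages for each no-RF patient, all of whom have already consented. Sites must record why RF was not delivered, and the sponsor must publish a second, lower success figure.

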### **3.2 Risks**

Most of the potential risks and complications associated with the everlinQ endoAVF System and procedure are similar to the risks expected for Chronic Kidney Disease (CKD) patients undergoing surgically created AVF or AVG procedures. The potential risks related to the everlinQ endoAVF Systems and procedure include but are not limited to:

- Aborted or longer procedure
- Additional procedures (interventions)
- Bleeding, hematoma (a solid swelling of clotted blood within the tissues) or hemorrhage (an escape of blood from a ruptured blood vessel)
- Bruising
- Burns
- Compartment syndrome (excessive bleeding, a hematoma that worsens and causes increased pressure in a muscle compartment within the access arm)
- Death (mostly due to CKD related complications not the everlinQ endoAVF device or procedure)
- Electrocution
- Embolism (blood clot or device piece)
- Failure to mature (AVF can never be used)
- Fever (pyrogenic reaction)
- Heart problems such as arrhythmias (abnormal beats) that can be caused due to high levels of potassium in the blood (mostly due to CKD and not the everlinQ endoAVF device or procedure)
- Increased risk of congestive heart failure (heart fails due to increased flow from AVF)
- Infection (local or in the blood (bacteremia))
- Numbness, tingling and/or coolness in the fistula extremity
- Occlusion
- Problem due to sedation or anesthesia
- Pseudoaneurysm (leaking hole in artery that forms blood clot on outside of it)
- Sepsis (systemic inflammatory reaction)
- Steal syndrome or ischemia (not enough blood flow to hand)
- Stenosis
- Swelling, irritation or pain
- Thrombosis
- Toxic or allergic reaction
- Venous hypertension (arm swelling)
- Vessel, nerve or AVF damage or rupture
- Wound problem

Cannulation risks that may occur in endo AVF are similar to the cannulation risks expected for patients undergoing surgically created AVF or AVG procedures. (e.g., fistula infiltration injury due to needle cannulation, clotting, etc.)

There may also be other potential risks related to use of the everlinQ endoAVF System and procedure that are unforeseen at this time.

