**Number of Patients Who Met Functional Cannulation:** Functional Cannulation is defined as 2-needle access of the endoAVF access circuit with performance of  $\geq 2/3$ rds of  $\geq 120$  minute dialysis sessions through the endoAVF access circuit over a continuous 28-day period.

**Central Venous Catheter (CVC) Exposure:** CVC exposure will be analyzed at the follow-up time points, presenting the number/percent of patients reporting CVC use and the number/percent reporting dialysis access through other means, as well as the number/percent of subjects not yet on dialysis.

**Adverse Events:** Rate of serious procedure or device related Adverse Events (AEs) throughout the study period. The relevant events and rates of occurrence will be analyzed with a time component, to analyze procedural AEs and post-procedural AEs.

**Intervention Rate:** The percentage of patients requiring intervention will be calculated at 3, 6 and 12 months follow-up visits post index procedure. The rate of interventions that occurred during the index procedure and during short term follow-up will also be calculated.

The endoAVF-related interventions include:

- Interventions to maintain or restore patency of the endoAVF, including endovascular and surgical procedures designed to address occlusive thrombosis (resulting in absence of thrill or bruit at endoAVF) and clinically significant occlusive stenosis at or near endoAVF site.
- Interventions to support maturation of the arterialized vein segments, including endovascular procedures such as secondary coil embolization to facilitate flow into the target cannulation veins.
- Interventions to support cannulation of the arterialized vein segments, including procedures such as a superficialization or elevation where the target cannulation vein is brought closer to the skin surface to enable cannulation, without the creation of a new AV fistula.
- Any intervention to address any complications or adverse events of the access circuit.

**Note:** Any additional procedure performed at the time of the index procedure to address an adverse event will require a Post-Procedure Intervention eCRF to be completed.

**Note:** Diagnostic fistulogram, angiogram or duplex ultrasound will not be considered an intervention for the purpose of this study.

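### The serious related adverse event rate leaves out consented patients who had a study catheter inserted but received no RF energy, and the plan specifies no adverse event collection for them

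*Combined protocol and SAP*

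**What the plan says.** Section 4.1 sets the entry rule: "Study candidates who undergo the everlinQ procedure (catheter insertion and delivery of RF energy) will be enrolled in the study". Candidates who do not undergo the procedure "will be treated per physician and hospital guidelines and will not be considered enrolled in the study". Section 5.2 labels every consented patient without the procedure a screen failure.

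Table 5-2 applies the rule. Its second row covers the case where "The study catheter was inserted but RF energy was not delivered and therefore, the patient did not undergo endoAVF procedure", with abortion of the procedure or conversion to surgery as examples. The stated action is a Screening Log entry, the same as in the first row, where no catheter was inserted. The third row (RF delivered, no fistula created) is handled differently: "Collect all baseline-procedure and adverse event data and exit the patient (end date = date of AE resolution".

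Section 4.3 restricts the outcome measures to enrolled patients without a renal transplant unless otherwise noted. The safety measure is "Rate of serious procedure or device related Adverse Events (AEs) throughout the study period", and no exception to that population is noted for it.

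Section 6.1 describes device exposure without mentioning RF: "The everlinQ device portion of the procedure only includes insertion, deployment and removal of the everlinQ catheters". Its causality categories begin with wording such as "The AE follows a reasonable timing from treatment (or attempted treatment) with the device". Section 3.2 includes "Aborted or longer procedure" in its list of risks.

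**The concern.** Patients in the second and third rows of Table 5-2 have both had the device in their vessels, and neither group leaves with an endoAVF. Only RF delivery separates them, yet one group has its adverse events recorded and followed and the other does not. An injury during catheter insertion that led the operator to stop would fall within the device portion as Section 6.1 describes it, but could not appear in the safety rate.

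This matters because the study is descriptive. Section 7 tests no hypotheses, so the reported rates are its product, and Section 4.2 says the data may support reimbursement and publications. A reader is likely to take the rate as the risk of having the procedure attempted. With at most 200 enrolled patients and probably few serious related events, a handful of uncounted events would change the figure. Procedure and event details not recorded at the time may be hard to recover later.

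**Working it through.** **Step 1: who is counted where.**

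| Situation (Table 5-2) | Device in vessel | Enrolled | Adverse event data specified | In the Section 4.3 rate |
|---|---|---|---|---|
| Row 1: consent, no catheter | No | No | No | No |
| Row 2: catheter, no RF | Yes | No | No | No |
| Row 3: RF, no endoAVF | Yes | Yes | Yes | Yes |
| Row 4: RF, endoAVF created | Yes | Yes | Yes | Yes |

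Row 2 is the only device-exposed group outside the rate.

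**Step 2: direction of the difference.** Let p be the event risk in RF-treated patients, q the risk in aborted attempts, and f the share of insertions stopped before RF. Then

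per-insertion rate = (1 − f)p + fq, and per-insertion rate − reported rate = f(q − p).

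The reported rate is too low as a per-attempt risk if q > p, equal if q = p, and too high if q < p.

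**Step 3: illustration.** The plan gives no expected event rate and no expected number of aborted attempts, so there is no figure to reproduce. Only the 200 comes from the documents. Assumed: p = 3% (6 events in 200), f = 5% or 10%, q = 10% or 20%. Insertions = 200/(1 − f), which gives 210.5 (10.5 aborted) or 222.2 (22.2 aborted).

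| f | q | Per-insertion rate | Uncounted events |
|---|---|---|---|
| 5% | 10% | 0.95 × 3% + 0.05 × 10% = 3.35% | 1.05 |
| 5% | 20% | 0.95 × 3% + 0.05 × 20% = 3.85% | 2.1 |
| 10% | 10% | 0.90 × 3% + 0.10 × 10% = 3.70% | 2.2 |
| 10% | 20% | 0.90 × 3% + 0.10 × 20% = 4.70% | 4.4 |

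In the last row the share of events missing is 4.4/(6 + 4.4) = about 43%, and the rate is understated by (4.70 − 3.00)/4.70 = about 36%. The two differ because the aborted patients are missing from the denominator too.

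If q = 3%, the rate stays at 3.0% and only 0.3 (10.5 × 3%) to 0.7 (22.2 × 3%) events are lost. If q = 0, the per-insertion rate is 2.85% (f = 5%) or 2.70% (f = 10%), so 3.0% slightly overstates it.

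**Step 4: whole patients, also assumed.** With 4 events in 200 the RF-treated rate is 2.0% (exact 95% CI 0.5% to 5.0%). Ten aborted attempts with 0, 1, 3 or 5 events give 4/210 = 1.9%, 5/210 = 2.4%, 7/210 = 3.3% or 9/210 = 4.3%. With 10 events in 200 (5.0%, CI 2.4% to 9.0%), twenty aborted attempts with 0, 2, 6 or 10 events give 10/220 = 4.5%, 12/220 = 5.5%, 16/220 = 7.3% or 20/220 = 9.1%. Most of these shifts lie inside the sampling interval, but that interval describes a different population and does not allow for the omission.

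**The case against.** The RF condition is stated consistently in Section 4.1 and Table 5-2, and a rate for RF-treated patients is a legitimate quantity if labelled as such. The device-portion sentence in Section 6.1 guides causality attribution; it does not define an analysis set. The attempted-treatment wording can be satisfied by the third row of Table 5-2, and the aborted-procedure entry in Section 3.2 does not say the abort precedes RF. A reader might infer a flat contradiction. What the documents show is a tension between where device exposure begins and where safety counting begins.

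A reader might also infer that these events are never collected or never adjudicated. No sentence says so. Table 8-1 requires reports of any serious adverse event and any serious or unanticipated serious device effect, without limiting this to enrolled patients, and Section 6.1 sends all reported events to the Clinical Events Committee. A serious insertion injury may therefore reach both. It would still not enter the Section 4.3 rate, and a non-serious event has no stated route.

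Finally, the attempts may not have been stopped by complications. Table 5-2 names no cause, and Section 5.2 expects some patients to be found anatomically ineligible at the index procedure. Section 6 also excludes some minor events, such as access-site hematoma that needs no endovascular or surgical intervention and does not affect discharge. These points stand, and they rule out any claim about the direction of bias. They do not remove the gap: without data on these patients, benign stops cannot be told apart from injuries. Section 5.2 does require the status of all screened patients to be logged, but the plan does not say that the log separates patients with a catheter inserted from those without.

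**Conclusion.** The point holds in this form: the plan specifies no adverse event form or follow-up for consented patients with a catheter inserted and no RF, and leaves them out of both parts of the serious related adverse event rate. The rate describes RF-treated patients only.

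A reader might go on to conclude that the reported rate is biased downward. The documents do not support that, because they give neither the number of aborted attempts nor the reasons for them. The range of 3.35% to 4.70% against 3.0% rests on assumed inputs that set the risk in aborted attempts at roughly three to seven times the RF-treated risk (10%/3% to 20%/3%). At equal risk there is no difference in the rate.

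This should be fixed, because the omission concerns device-exposed patients in the study's safety outcome and the repair is small. It does not touch the patency analyses or any hypothesis test.

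**What to change.** - **Table 5-2, second row:** keep these patients outside the enrolled (RF) set, but add the data action of the third row: collect procedure and adverse event data, record reportable events until they resolve, and send them to the Clinical Events Committee.
- **Section 4.3, Adverse Events:** report the serious related rate on all consented patients with at least one study catheter inserted, beside the rate in RF-treated patients. Give the number of aborted attempts and the reason for each.
- **Sections 4.1, 4.3 (population sentence) and 5.2:** align the wording so that screen-failure status no longer implies absence from the safety count. State in Table 8-1 whether its reports cover these patients.

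Cost: procedure and adverse event forms for a small number of already consented patients (about 10 to 22 on the assumptions above), and a protocol amendment, which Section 8.4 makes subject to sponsor and EC approval. The published rate may look less favourable. The enrolled set stays as it is.
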